1 DEFINITIONS

Term	Definition
Adverse Event (AE)	Any untoward medical occurrence, unintended disease or injury, untoward clinical signs (including abnormal laboratory findings) in subjects, users or other person, whether or not related to the medical device.
Engel Classification	 Class I: Free of disabling seizures IA: Completely seizure-free since surgery IB: Non disabling simple partial seizures only since surgery IC: Some disabling seizures after surgery, but free of disabling seizures for at least 2 years ID: Generalized convulsions with antiepileptic drug withdrawal only Class II: Rare disabling seizures ("almost seizure-free") IIA: Initially free of disabling seizures but has rare seizures now IIB: Rare disabling seizures since surgery IIC: More than rare disabling seizures after surgery, but rare seizures for at least 2 years IID: Nocturnal seizures only Class III: Worthwhile seizure reduction IIIA: Worthwhile seizure-free intervals amounting to greater than half the follow-up period, but not less than 2 years Class IV: No worthwhile improvement IVA: Significant seizure reduction IVB: No appreciable change IVC: Seizures worse
ILAE (International League Against Epilepsy) Classification	 Class 1: Completely seizure free; no auras Class 2: Only auras; no other seizures Class 3: 1 to 3 seizure days per year; ± auras Class 4: 4 seizure days per year to 50% reduction of baseline seizure days; ± auras Class 5: Less than 50% reduction of baseline seizure days; ± auras Class 6: More than 100% increase of baseline seizure days; ± auras
Index Procedure	First NeuroBlate [®] System procedure after signing the LAANTERN Informed Consent Form.

Term	Definition

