5 STUDY DESIGN OVERVIEW

This is a prospective multi-center registry that will include data collection at baseline (prior to NBS procedure, which is also referred as the index procedure), index procedure, discharge and up to 5 years of follow-up including data from additional NBS procedures. Up to 3,000 subjects may be enrolled at up to 50 study sites. Some subjects may be enrolled in sub-studies associated with LAANTERN as per site participation and sub-study specific consent.

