5.1 STUDY OBJECTIVES

Objective 1: Safety

Observe safety profile described by NBS or surgical-related SAEs

Objective 2: Reason for NeuroBlate®

Objective 3: Procedural Outcomes

- Local Control
- Progression Free Survival
- Overall Survival
 - Seizure Freedom
 - Engel and ILAE Classification

Objective 4: Cognitive & Quality of Life Outcomes

Collected for subjects based on their disease etiology and age.

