5.2 STUDY POPULATION

Subjects who meet inclusion criteria and no exclusion criteria and sign the Informed Consent Form (ICF) (CL10030) will be considered enrolled in this study. At the time of enrollment, a unique identification number (ID) will be assigned to the subject and used to collect all study information via electronic Case Report Forms (eCRFs).

Inclusion Criteria:

- 1. Subject or legally authorized representative provides written authorization and/or consent
- 2. Subject who is to undergo thermal therapy by the NeuroBlate[®] System for treatment of their neurological disorder

Exclusion Criteria:

- 1. Subject who is, or is expected to be inaccessible for follow-up
- 2. Other concurrent medical or other condition (chronic or acute in nature) that, in the opinion of the investigator, may prevent participation or otherwise render patient ineligible for the study

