6 INFORMED CONSENT (ICF)

The Sponsor will provide a template ICF to each site for IRB submission prior to the site initiation. This template may be modified to suit the requirements of the individual study site. The Sponsor must preapprove all changes to the ICF prior to initial submission to the IRB. A copy of the IRB-approved ICF must be sent to the Sponsor and the original copy must be retained at the study site. If the ICF is amended by the reviewing IRB, the Sponsor must pre-approve all changes to the ICF prior to submission. In addition, a copy of the approved documents must be provided by the Investigator to the Sponsor prior to enrollment of subjects in the study.

The Investigator or assigned designee must administer this approved ICF to each prospective study subject and obtain the subject's signature or a legally authorized representative signature along with the date of consent prior to enrollment in the study. The ICF must be obtained in accordance with 21 CFR Part 50. Subjects must be informed about their right to withdraw from the study at any time and for any reason without sanction, penalty, or loss of benefits to which the subject is otherwise entitled and informed that withdrawal from the study will not jeopardize their future medical care. A copy of ICF must be given to each subject enrolled in the study. The institutional standard subject consent form does not replace the study ICF.

[figure not shown]

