7 STUDY VISITS

A subject follow-up schedule is intended to align with typical standard of care practices. Data may be collected during in-office subject visits or remotely (e.g. telephone, email, or mail), when feasible and appropriate. These modes of data collection aim to help facilitate robust and reliable long-term surveillance and survival data collection. For this standard of care registry, the visit windows are continuous, however target visit dates are provided below. Visits should be completed near the target visit date or be the most complete visit within the visit window. A visit window tool is available in the EDC system. Figure 1 indicates the sequence of subject visits.

Target Visit Dates:

- Baseline within 60 days prior to the Index Procedure
- Index Procedure Day 0
- Discharge N/A
- 1 Month Follow-up Visit Day 30
- 3 Month Follow-up Visit Day 90
- 6 Month Follow-up Visit Day 180
- 1 Year Follow-up Visit Day 365
- 2 Year Follow-up Visit Day 730
- 3 Year Follow-up Visit Day 1095

- 4 Year Follow-up Visit Day 1460
 5 Year Follow-up Visit Day 1825

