7.3 ADDITIONAL NEUROBLATE PROCEDURES

In the case additional NeuroBlate[®] procedures are performed following the index procedure, this information will be collected on the Additional Procedure form. Any adverse events associated with these procedures will be collected on an Adverse Event form. Patient follow up schedule is based on the index procedure date. Procedure data and reportable adverse events will be collected on all additional NeuroBlate[®] System procedures completed after the Index Procedure.

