Statistical Plan
June 2020

NCT02392078

LAANTERN Statistical Methods

General Summary

Descriptive statistics will be used to summarize the patient population data, operative data, and follow-up data. For continuous variables, the total count, mean, standard deviation, minimum, and maximum will be provided. For categorical variables, the total count and percentage will be provided.

Survival Analysis with Censoring/Truncation

The survival analysis will be used to estimate time-to-event probability and will take into account right-censoring or left truncation. Left truncation occurs when patients are enrolled into the study after the NBS Index Procedure occurs. The survival function will be estimated using the Kaplan-Meier method. The hazard rate over time may be provided along with corresponding 95% confidence limits to assess potential time-dependent trends.

Comparative Analysis

Comparisons in survival/event rates may be made between subgroup of patients with various disease states (for example, epilepsy vs tumor, etc.), differences in baseline demographics, product models (for example, new device iterations, etc.), or other factors that are deemed important for understanding patient outcomes or risk.

Proportional Hazards Regression

The proportional hazards regression models may be used for time-to-event analysis. Predictors may include patient baseline variables in addition to the risk factor of interest.

Determination of Patients for Analysis

All enrolled patients who had procedures with the NBS will be included in this analysis. Additional analyses may be performed for subgroups of interest based on all enrolled patients with valid data.

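### The SAP provides for patients enrolled after the Index Procedure, which the protocol rules out, and nothing keeps any such patients out of its plain percentages

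*SAP*

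**What the plan says.** **Protocol.** Four places put consent and enrolment before the procedure.

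- Section 1 defines the Index Procedure as the first NeuroBlate "System procedure after signing the LAANTERN Informed Consent Form".
- Section 5 describes a prospective registry with data collected at "baseline (prior to NBS procedure, which is also referred as the index procedure").
- Section 5.2 counts a subject as enrolled once the criteria are met and the consent form is signed. The second inclusion criterion looks forward: "Subject who is to undergo thermal therapy by the" NeuroBlate System.
- Section 7 sets "Baseline within 60 days prior to the Index Procedure".

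Section 6 adds that the signature is obtained "along with the date of consent prior to enrollment in the study". Section 7.3 fixes the clock: "Patient follow up schedule is based on the index procedure date".

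**SAP.** Under Survival Analysis with Censoring/Truncation, the survival analysis is to allow for right-censoring or left truncation, and the latter is explained thus: "Left truncation occurs when patients are enrolled into the study after the NBS Index Procedure occurs". Under Determination of Patients for Analysis, the set is everyone enrolled who had an NBS procedure. It has no condition on whether consent came before or after. Under General Summary, categorical data get a count and a percentage, with no mention of late entry.

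**The concern.** The two documents disagree about who can be in the registry. Under the protocol nobody is enrolled after their Index Procedure, yet the SAP defines a statistical problem by patients who are.

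This matters beyond wording because the allowance for late entry stops at the survival section. The first protocol objective is safety: "Observe safety profile described by NBS or surgical-related SAEs". Section 10 states that there is no hypothesis and that analysis is descriptive, so plain percentages are a main form of safety output. A patient who consents after the procedure must have survived, and been well enough to enrol, up to that moment. Such a patient adds to the denominator but cannot contribute a death, or an event that prevents enrolment, from before consent. Percentages of those early events would be too low, which favours the device.

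Baseline summaries would be affected in a different way: late-consented patients are a selected group, and nothing was collected prospectively from them before the procedure.

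**Working it through.** **Step 1. Compare the texts.** The documents give no count, rate or sample-size calculation on this point, so there is no plan figure to reproduce. By the Protocol section 1 definition, the Index Procedure follows consent. By section 5.2, enrolment requires a signed consent form and a procedure still to come. Section 7.5 lists not having the procedure as a reason for withdrawal, which again puts enrolment first. A patient treated once before consent and again afterwards is no exception, because the later procedure is then the Index Procedure. The group in the SAP sentence is therefore empty under the protocol's rules.

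**Step 2. Derive the bias if the group is not empty.** Let

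- r = true risk of an early related death (or of an early related event that prevents enrolment), assumed equal in both groups;
- f = late-consented share of the analysed patients;
- q = share of the early risk already past when the late patients consent.

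The late patients' remaining risk is (r − qr)/(1 − qr), which is about (1 − q)r when r is small. Then

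crude percentage ≈ (1 − f)r + f(1 − q)r = r(1 − fq).

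The relative understatement is about fq. It is at most about f, reached when every late consent falls after the event window (q = 1).

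**Step 3. Illustrate the upper bound.** N = 3,000 is the enrolment maximum in Protocol section 5. The values of r and f are assumptions, not estimates for this registry. Each cell shows the crude percentage r(1 − f), then the shortfall N × f × r in deaths.

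| True r (expected deaths N × r) | f = 1% | f = 5% | f = 10% |
|---|---|---|---|
| 0.5% (15) | 0.495%; 0.15 | 0.475%; 0.75 | 0.450%; 1.5 |
| 1% (30) | 0.99%; 0.3 | 0.95%; 1.5 | 0.90%; 3 |
| 2% (60) | 1.98%; 0.6 | 1.90%; 3 | 1.80%; 6 |

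**Step 4. Compare with sampling error.** SE = √(r(1 − r)/N) gives 0.13, 0.18 and 0.26 percentage points at r = 0.5%, 1% and 2%. The bias rf equals one SE when f = √((1 − r)/(rN)), that is at f = 25.8%, 18.2% and 12.8%. Below those shares the bias is less than one standard error.

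**Step 5. Test the equal-risk assumption.** Suppose the risk is 1% in patients who consented beforehand and 2% in the population from which late consenters come, with f = 10%. The overall risk is 0.9 × 1% + 0.1 × 2% = 1.1%. The crude figure is 0.9 × 1% = 0.9%, an understatement of 0.2/1.1 = 18%, which exceeds f. Restricting to prior consent gives 1.0%. That is closer, but still not the risk for the whole treated group. The bound in step 2 therefore needs equal risk.

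**Step 6. Cost of restricting.** Dropping a share f from the denominator multiplies the standard error by 1/√(1 − f): 1.005, 1.026 and 1.054 at f = 1%, 5% and 10%.

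**The case against.** The strongest reply is that the SAP sentence only explains a term. It neither permits late enrolment nor reports any, and a SAP may provide for something the protocol does not allow. Protocol section 9 anticipates improper consenting as a deviation and sends all deviations to the sponsor, and consent signed after the procedure could plausibly fall under that. Protocol section 5.2 can also be read to exclude late-consented patients from the word enrolled, and then the SAP's analysis set excludes them too. Both replies are fair. They show that the plan has a harmless reading, but not that this reading is the one in force: the SAP itself calls these patients enrolled and sets no condition on timing. If the SAP's rule on which patients are analysed is meant for the survival analysis alone, the descriptive percentages have no stated analysis set.

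A reader might infer more than the documents support:

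- **That the registry contains late-enrolled patients, or that its safety percentages are biased.** No document gives a count or shows that one such patient exists.
- **That follow-up of such patients would have no time origin.** Section 1 taken alone suggests this. Section 5, however, treats the NBS procedure and the index procedure as the same thing, so a usable date exists. The SAP simply does not name it.
- **That truncation is ignored.** The survival section does provide for it.
- **That all SAE percentages are affected.** Non-fatal events that do not prevent enrolment are not necessarily affected.

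A version difference is also possible. The SAP is dated June 2020 and the supplied protocol text shows no date.

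**Conclusion.** The point stands in a limited form. As supplied, the SAP and protocol conflict on whether anyone can be enrolled after the Index Procedure, and the SAP neither restricts nor adjusts its plain percentages for such patients. That much is certain from the text, although different document versions may explain it.

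The bias is conditional. It is zero if the protocol was followed. Otherwise it lowers crude percentages of early related deaths, and of early related events that prevent enrolment, by a relative amount of at most about f. This assumes equal underlying risk in the two groups; if late-consenting patients come from a higher-risk population, the understatement can exceed f. On the assumed inputs the absolute effect is small at low f. Severity is minor to moderate.

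**What to change.** Reconcile the SAP with the protocol, and add to the SAP:

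1. **Denominator.** Base crude early-event and baseline percentages on patients whose consent date is on or before the date of the NBS procedure that led to their enrolment. Where the dates are the same, check the order from source. The rule should not refer to the Index Procedure: Protocol section 1 already defines that as following consent, so every patient who has one would pass.
2. **Late-consented patients.** Report their number, and list their SAEs separately so that no event is lost. Use these patients only in time-to-event analyses, with time zero at that NBS procedure and delayed entry at consent.
3. **Left-truncation sentence.** It may stay as a contingency if it is reworded to cover consent deviations.

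The cost is SAP wording, one comparison of consent and procedure dates, and one SAE listing if any late-consented patients are found. Treatment, visits and data collection do not change. The downside is a slightly smaller denominator, with standard errors about 0.5%, 2.6% and 5.4% wider at f = 1%, 5% and 10%. Under unequal risk, the restricted percentage describes patients who consented beforehand rather than everyone treated, and the report should say so.

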7.5 STUDY COMPLETION OR WITHDRAWAL

Subjects will complete the study once their 5-year follow-up visit is completed or if the subject was prematurely withdrawn prior to their 5-year visit.

The subject may be prematurely withdrawn from the study for the following reasons:

- Subject did not have NeuroBlate[®] Procedure.
- Subject Lost to Follow-up: All efforts shall be made to document at least 3 attempts to contact subject, which would include a certified letter to the subject. If attempts to contact the subject fail, the subject may be withdrawn from the study and considered lost to follow up.
- Subject Withdrawal: A subject may voluntarily withdraw from the study at any time.
- Investigator Withdrawal of Subject: An Investigator may withdraw a subject for reasons which may include noncompliance, failure to keep appointments, etc.
- Subject Death: If subject passed away, the expiration date will be considered the end of study date. All feasible attempts should be made to confirm date of death, as this is key for overall survival analysis.

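### The SAP names only Kaplan-Meier and gives no rule for death in local control; if deaths are censored, 1 minus Kaplan-Meier overstates the proportion of patients whose lesion fails

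*SAP*

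**What the plan says.** The SAP section on survival analysis with censoring and truncation sets its aim as follows: "The survival analysis will be used to estimate time-to-event probability and will take into account right-censoring or left truncation". The only estimator it names is in the next step: "The survival function will be estimated using the Kaplan-Meier method". It assigns no endpoint to this analysis. Neither document mentions competing events or cumulative incidence.

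Two later SAP sections build on it, both optional. Under Comparative Analysis: "Comparisons in survival/event rates may be made between subgroup of patients with various disease states"; device models and baseline factors are also listed there. Under Proportional Hazards Regression: "The proportional hazards regression models may be used for time-to-event analysis". No cause-specific or subdistribution form is specified.

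Protocol section 5.1, Objective 3, lists "Local Control" as an outcome separate from progression-free survival and overall survival. The protocol defines neither local control nor progression-free survival. Section 5 plans "up to 5 years of follow-up". On death, section 7.5 says: "If subject passed away, the expiration date will be considered the end of study date". It links the death date to one use only: "All feasible attempts should be made to confirm date of death, as this is key for overall survival analysis".

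**The concern.** A patient who dies with the treated lesion controlled can no longer have a local failure. The only device the SAP offers for follow-up that ends without the event is right-censoring. In a time-to-local-failure analysis, that patient would therefore by default be censored at death.

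Kaplan-Meier then treats the patient as someone who could still fail later, at the same rate as those still at risk. One minus Kaplan-Meier becomes a net quantity: the failure probability if nobody died first, and even that needs death and local failure to be independent. It is not the probability that a treated patient's lesion fails, which is the natural reading of the SAP's stated target, a time-to-event probability.

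The gap grows with mortality and with length of follow-up. The registry follows patients for up to 5 years, includes brain malignancy, and has overall survival as an outcome, so deaths are expected. The gap would also differ between disease states with different mortality, which is one of the comparisons the SAP allows.

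**Working it through.** **The plan's own figure.** There is none to reproduce. The documents give no local-failure rate, mortality rate or planned precision. All rates below are assumptions and serve only to show the size.

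**Assumed inputs**
- Constant, independent hazards.
- F12, the 12-month failure probability with deaths censored: 20%, 30%, 40%.
- m, the median time to death without local failure: 9 to 60 months, plus the case of no deaths.

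**Formulas**
- Local-failure hazard: λL = −ln(1 − F12)/12
- Hazard of death without local failure: λD = ln 2/m
- Deaths censored: 1 − KM(t) = 1 − exp(−λL·t)
- Proportion that fails: CIF(t) = λL/(λL + λD) × [1 − exp(−(λL + λD)·t)]

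**Middle case, F12 = 30%, m = 24 months**
- λL = −ln(0.70)/12 = 0.02972; λD = ln 2/24 = 0.02888; sum 0.05860; ratio λL/sum = 0.5072
- 12 months: 1 − KM = 30.0%; CIF = 0.5072 × (1 − 0.4950) = 25.6%; excess 4.4 points
- 24 months: 1 − KM = 51.0%; CIF = 0.5072 × (1 − 0.2450) = 38.3%; excess 12.7 points

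**Excess of 1 − KM over CIF, in percentage points**

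| F12 | 12 months, m = 9 | 12 months, m = 60 | 24 months, m = 9 | 24 months, m = 60 |
|---|---|---|---|---|
| 20% | 6.7 | 1.3 | 18.5 | 4.2 |
| 30% | 9.9 | 1.9 | 25.3 | 5.7 |
| 40% | 12.9 | 2.4 | 30.4 | 6.8 |

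With no deaths the excess is 0 throughout. At 60 months, the end of the registry's follow-up, the same grid gives 15.7 to 56.7 points.

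**Starting from overall survival instead.** Let the death hazard be λD before local failure and k·λD after it, with k = 1, 2, 3 or 5 (assumed). Overall survival is then

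S(t) = exp(−(λL + λD)t) + λL × [exp(−kλD·t) − exp(−(λL + λD)t)]/(λL + λD − kλD).

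Solve for λD so that S equals 0.5 at the chosen median. The 24-month excess at F12 = 30% is:

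| Median overall survival | k = 1 | k = 2 | k = 3 | k = 5 |
|---|---|---|---|---|
| 12 months | 21.2 | 19.4 | 18.3 | 16.8 |
| 24 months | 12.7 | 10.5 | 9.2 | 7.6 |

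Over F12 = 20% to 40% the range is 13.5 to 25.4 points for a 12-month median and 6.7 to 15.1 points for a 24-month median.

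**Two groups with the same local-failure hazard.** Take F12 = 30% in both, with m = 12 months in one group and 36 months in the other. At 24 months Kaplan-Meier gives 51.0% in both, and the cause-specific hazard ratio is 1. The proportions that fail are:
- m = 12: λD = 0.05776, CIF = 29.8%
- m = 36: λD = 0.01925, CIF = 42.0%

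**Check by simulation.** F12 = 30%, m = 12, 200,000 patients, 30% of them entering uniformly 0 to 6 months late, with delayed-entry risk sets. At 24 months 1 − KM was 50.9% and Aalen-Johansen 29.8%; the closed forms give 51.0% and 29.8%. The excess therefore remains when left truncation is handled correctly.

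**The case against.** The strongest reply is that the criticised analysis is not written in the plan. The SAP names no endpoint, and Kaplan-Meier is right for overall survival and for progression-free survival with death as an event. Protocol section 10 describes a descriptive study with no hypothesis. Table 1 schedules MRI only around the index procedure, so local control may well be a simple proportion. The end-of-study rule in section 7.5 is administrative and is not a censoring rule. One minus Kaplan-Meier is a legitimate net quantity under independence, and a cause-specific comparison is a valid choice for comparing groups. Every rate used above is assumed.

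Much of this stands, and it is why the point is conditional. Censoring at death is an inference from the SAP's silence. In the two-group example the hazard ratio of 1 is the correct answer to the question about hazards. The size cannot be established from the documents.

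It does not remove the point. The main product of a descriptive registry is its estimates, so a reader has to know which quantity each estimate targets. If local control is meant as a proportion or as a composite with death, the plan does not say so. The direction of the excess does not depend on the assumed rates: it is upward whenever deaths occur before local failure.

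**Conclusion.** The concern holds in its conditional form. If local control is analysed as time to local failure with the one estimator the SAP names, and deaths are censored, the reported failure percentage will exceed the proportion of treated patients whose lesion fails. Under the assumed rates the excess ranges from about 1 point (12 months, low mortality) to about 30 points (24 months, high mortality and high failure). It is negligible where deaths before local failure are rare.

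The point does not touch overall survival, progression-free survival with death as an event, or a percentage reported at a visit. It is an improvement that should be made, not a flaw that invalidates the plan. Confidence is medium, because the plan leaves the endpoint undefined.

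**What to change.** In the SAP:

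1. Define the local-failure event and its time origin, and state how death without local failure is handled.
2. If local control is analysed as time to local failure, estimate its probability with the Aalen-Johansen cumulative incidence function, with death without local failure as the competing event. Give 95% confidence limits, and use delayed-entry risk sets so that left truncation is still allowed for.
3. Keep Kaplan-Meier for overall survival, and for progression-free survival with death stated as an event.
4. For comparisons between disease states or device models, report cause-specific hazard ratios beside the cumulative incidence curves and say which question each answers.
5. Extend this to another event only if it is analysed as time-to-event and death precludes it.

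The cost is a few sentences and standard software; death dates are already sought for overall survival. The drawback is less direct comparability with published Kaplan-Meier figures for local control. A supplementary Kaplan-Meier curve, labelled as the net quantity with deaths censored, deals with that.

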8.1 REPORTING OF ADVERSE EVENTS BY CLINICAL SITES

The following adverse events (AE) are considered reportable for this study, as determined by PI discretion:

NeuroBlate[®] System related AEs

• Adverse events related to the NeuroBlate® System Device (i.e. probe, robotic probe driver, software)

NeuroBlate[®] Procedure related AEs

 Adverse events that occur due to a NeuroBlate[®] (LITT) procedure and cannot be directly attributed to the NBS Device or surgical procedure

Surgical Procedure related AEs

• Adverse events that occur due to the surgical procedure and cannot be directly attributed to NeuroBlate[®] System or procedure (i.e. biopsy related event)

The following adverse events are considered not reportable for this registry:

- Planned hospitalization for a pre-existing condition without serious deterioration in health.
- Any expected postoperative complaints or symptoms such as pain at biopsy site, headaches, weakness, cerebral edema, and transient events (less than 30 days from procedure) that do not require intervention. If the event involves a clinically significant change in severity or duration of symptoms or requires clinical intervention that is different from ordinary postoperative care, the event is considered a reportable AE.

Reportable AEs must be described by duration (start and resolution dates), relationship to the NeuroBlate[®] System or surgical procedure, action taken to resolve the event, and outcome of the event. Additional information, such as procedural notes, treatment notes, or clinical summary may be requested as supporting documentation.

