8.2 ADVERSE EVENT RELATEDNESS

The relationship of the AE to the NeuroBlate[®] System Device (NBS) or the NeuroBlate[®] (LITT) procedure or surgical procedure will be determined by the Primary Investigator (PI) based upon the following definitions.

Definite: The AE follows a reasonable temporal and causative sequence from receipt (or attempted receipt) of the device treatment or procedure.

Possible: The AE follows a reasonable temporal sequence from receipt of the device treatment or procedure and the possibility of device treatment or procedure involvement cannot be excluded. However, other factors such as underlying disease, concomitant medications, or concurrent treatment are presumable.

Not Related: The AE has no temporal sequence from receipt of the device treatment or procedure, or it can be explained by other factors, including underlying disease, concomitant medication, or concurrent treatment. Note: If the event is determined to be "Not Related" to either the NBS or the Surgical Procedure, it is not considered a reportable AE.

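### Subjects operated on without any use of the NBS fall outside the analysis set, although Objective 1 counts surgical SAEs

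*SAP*

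**What the plan says.** The SAP, under Determination of Patients for Analysis, gives one main set: "All enrolled patients who had procedures with the NBS will be included in this analysis". It adds an optional provision: "Additional analyses may be performed for subgroups of interest based on all enrolled patients with valid data". No separate safety set is defined in either document.

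Protocol section 7.5 introduces its list with "The subject may be prematurely withdrawn from the study for the following reasons", and the first entry is "Subject did not have NeuroBlate[®] Procedure". Under section 5.2, enrolment happens at consent, so a subject is enrolled before anyone knows whether the NBS will be used.

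The safety objective reaches further than the set. Objective 1 (section 5.1) covers SAEs related to the NBS or to the surgery. Section 8.1 makes purely surgical events reportable in their own right: "Adverse events that occur due to the surgical procedure and cannot be directly attributed to" the NBS or its procedure, with a biopsy event as the example. In section 8.2, the Definite category applies to events after "receipt (or attempted receipt) of the device treatment or procedure".

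Section 1 defines the Index Procedure as the first NeuroBlate "System procedure after signing the LAANTERN Informed Consent Form". It does not say at what point such a procedure has begun.

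**The concern.** The events that Objective 1 sets out to describe include harm from the surgery itself. The set over which they will be summarised depends on whether the NBS was used. A subject can be exposed to the first without the second, and the plan has no rule for that subject.

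This matters because the exclusion may depend on the outcome. If surgery is stopped because of a complication before the NBS is used, the complication is both the SAE of interest and the reason the subject leaves the set. The reported proportion would then be too low. The documents do not say why or how often cases are stopped, so this is a possible mechanism and not an observed one. Protocol section 10 states that there is no hypothesis and that analysis is descriptive. The SAE proportion is therefore itself the result, and its denominator has to be reproducible across up to 50 sites.

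**Working it through.** **Step 1: place each kind of case against the text.** There is no sample size, power or event figure to reproduce; the 3,000 in section 5 is an enrolment cap. The check is mainly one of reading.

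| Case | Withdrawal under 7.5? | In the SAP set? | Surgical SAE within Objective 1? |
|---|---|---|---|
| A. Consented, no procedure started | Allowed | No | None can arise |
| B. Surgery started (e.g. burr hole or biopsy), NBS never used | Allowed | No | Yes |
| C. Probe placed, no laser energy delivered | Not stated | Probably: section 4 counts the probe as an NBS component | Yes |
| D. Ablation started, not completed | No text allows it for this reason | Yes on the ordinary reading | Yes |
| E. Ablation completed | No | Yes | Yes |

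The firm gap is case B. Case C is unclear. Cases D and E are not affected.

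**Step 2: AE collection in case B.** Table 1 starts AE collection at the Index Procedure, and section 7 dates the visits from it as Day 0. If no NBS procedure took place, there is no Index Procedure as section 1 defines it. The AE schedule then has no stated starting date for that subject.

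**Step 3: possible size, as illustration only.** Let q be the share of operated subjects left out, rc the SAE proportion in those kept, and ra the SAE proportion in those left out.

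- SAE proportion among all operated = (1 − q) × rc + q × ra
- Understatement when only rc is reported = q × (ra − rc)

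The documents give none of these inputs. The assumed ranges are q from 0.5% to 5%, rc of 5% or 10%, and ra from rc up to 40%. The 3,000 cap is treated as the number operated, which is also an assumption.

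- Equal risk (ra = rc): understatement = q × 0 = 0 for any q. Events are still lost from the count: at q = 0.5% and rc = ra = 5%, 15 × 0.05 = 0.75 of a subject.
- Middle example (q = 2%, rc = 5%, ra = 20%): 3,000 × 0.02 = 60 subjects left out, and 60 × 0.20 = 12 of them with an SAE. The proportion among all operated is 0.98 × 5% + 0.02 × 20% = 5.3%, against 5.0% in the restricted set, a difference of 0.3 points.
- Upper end (q = 5%, rc = 5%, ra = 40%): 150 subjects left out, 60 with an SAE. The understatement is 0.05 × (40% − 5%) = 1.75 points, that is 6.75% against 5.0%.

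Over these ranges the understatement runs from 0 to 1.75 percentage points. The upper end combines the most extreme inputs and assumes that every subject counted in q is in fact left out.

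**The case against.** The best reply is that this is an undefined term and not a contradiction. If an attempted case counts as a procedure with the NBS, the SAP set and the relatedness rule in section 8.2 agree, and the reference there to attempted receipt favours that reading. Section 8.1 sorts events by cause and does not define who had a NeuroBlate procedure. The background in section 3 even describes the opening in the skull as part of working with the NBS. Withdrawal under section 7.5 is optional. Reportable SAEs go to the sponsor, preferably within 48 hours of discovery (section 15), so the records would exist. The SAP also permits further analyses of enrolled patients with valid data.

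Much of this stands. A reader might infer that every subject without a completed ablation is excluded and that the SAEs of those subjects are removed. The documents do not support that. Completion of the ablation is nowhere a condition for inclusion or withdrawal. Subjects with a started ablation, and probably those with a placed probe, are in the set on the ordinary reading. No text deletes an SAE already reported.

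The reply does not close case B. A background description does not fix an analysis set. Attempted receipt appears only in the Definite category, as a rule for judging events and not for choosing subjects. A reported SAE in a subject outside the set has no assured place in the Objective 1 summary, and the further analyses are optional and meant for subgroups. The lack of a hypothesis means that no test is affected, but the descriptive proportion still needs a stated denominator.

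**Conclusion.** The point holds in a narrow form. A subject whose surgery was started but in whom the NBS was never used can be withdrawn and falls outside the only main analysis set, although surgical SAEs belong to Objective 1. For cases stopped after probe placement, inclusion is likely but unstated.

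The bias is downward only if subjects left out carry a higher SAE risk than those kept, as they would if a complication is why the NBS was not used. The documents contain neither the frequency of such cases nor any SAE rate, so the size cannot be derived. The 0 to 1.75 percentage points above rest wholly on assumed inputs and should not be quoted as an estimate. The case for changing the text is that the exclusion can depend on the outcome and is cheap to prevent.

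**What to change.** - **SAP, analysis sets.** Define the Objective 1 safety set as all enrolled subjects in whom the surgical procedure for the NBS was started, whether or not the NBS was used or laser energy delivered. Name the event that marks the start, so that all sites apply the same rule. Keep the NBS-treated set for Objective 3 outcomes.
- **Protocol section 7.5.** Limit the withdrawal reason to subjects in whom no procedure was started.
- **Retention of events.** State that SAEs reported up to any withdrawal are kept in the safety summary.
- **Data collection.** Collect reportable AEs for operated subjects without NBS use on the existing schedule through the 1-month visit. Date it from the start of surgery, since these subjects have no Index Procedure as now defined.
- **Reporting.** Give operated subjects without ablation as a separate count, so that readers can see both denominators.

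The cost is a few sentences in the two documents and short AE follow-up of a few more subjects. Reported SAE rates may rise slightly. No treatment or procedure changes.
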